## 5.7. Primary Variables

### 5.7.1. Adverse Events

Adverse events will be classified using MedDRA version 20.1 classification system. The severity of adverse events will be graded by the investigator according to the CTCAE, Version 3.0 whenever possible. A treatment-emergent adverse event (TEAE) is defined as an adverse event that occurs or worsens in the period extending from the day of a subject's first dose of study drug to 6 weeks after the last dose of study drug in this study.

If a subject has multiple events under any given SOC and PT, the subject will be counted only once under that SOC and PT. If a subject has the same AE on multiple occasions, the highest severity (fatal, life-threatening, severe, moderate, and mild) recorded for the event will be presented and the highest drug relationship (1 = 'Unrelated', 2 = 'Unlikely', 3 = 'Possibly', 4 = 'Probably', 5 = 'Related'), reclassified into Related ('Possibly Related', 'Probably Related', 'Related') or Not Related ('Unrelated' and 'Unlikely'), will be presented on the respective tables.

Total numbers of AEs, TEAEs and serious AEs (SAE) and the number and percentage of subjects experiencing  $\geq 1$  TEAE,  $\geq 1$  SAE, discontinuation due to AE, and death will be tabulated. The number and percentage of subjects with TEAEs and SAEs will be by relationship to study drug and CTCAE/severity, respectively.

The number and percentage of subjects experiencing a specific TEAE will be tabulated

- 1) by SOC, and PT
- 2) by SOC, PT, and CTCAE/severity grade
- 3) by SOC in the descending order of the SOC frequency overall group,
- 4) by PT in the descending order of the PT frequency in overall group.

The following TEAEs will be analyzed similarly:

- 1) by SOC, and PT and

- 2) by SOC, PT, and CTCAE/severity grade.
- Possibly or probably treatment-related TEAEs
  - Serious TEAEs and possibly or probably treatment-related serious TEAEs
  - TEAEs leading to discontinuation from treatment
  - Adrenal, hepatic and renal events leading to special diagnostic evaluations TEAEs and possibly or probably treatment-related hepatic and renal TEAEs leading to special diagnosis evaluation
  - TEAEs with CTCAE/severity grade  $\geq 3$  and possibly or probably treatment-related TEAEs with CTCAE/severity grade  $\geq 3$
  - Common TEAEs (subject frequency of  $\geq 5\%$ )

Listings of death, serious AEs, AEs leading to discontinuation from treatment, and hepatic and renal AEs leading to special diagnostic evaluations will be provided.

The drug exposure adjusted TEAE incidence rate will be summarized by SOC and PT, where the incidence rate of the TEAE per 100 patient-year = (number of events/number of patient-years) \*100. The number of patient-years is defined as the sum of the number of days on study drug of all patients divided by 336. That is, a year is defined as 48 weeks.

In addition, the number of subjects with clinical laboratory abnormalities, abnormal vital signs, and abnormal electrocardiogram reported as TEAE will be summarized.

Non-serious TEAE will be displayed by SOC and PT. The common non-serious TEAE (subject frequency of  $\geq 5\%$ ) will also be displayed by SOC and PT.

Numbers of occurrence of serious TEAE and the numbers of occurrence of non-serious TEAE will be summarized by SOC and PT, separately.

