6.1.5. Return of Study Drug

Patients should return all remaining study drug (all unused sachets) to the study site at the end of each 12-week treatment period for inventory. The Study Drug Administration Record will serve as the source document for drug supply to the patients and will document the return of any unused drug for compliance assessments.

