10.4.3. Primary Variables – Safety

Vital signs (height, weight, systolic and diastolic blood pressure, radial pulse rate, and body temperature) and physical examination data will be listed and summarized by visit and overall. Where appropriate, changes from baseline at each visit will be summarized and tested by means of the paired t-test or a nonparametric alternative.

Adverse events will be classified using the MedDRA classification system. The severity of adverse events will be graded according to the CTCAE, Version 3.0, whenever possible.

The frequency of patients experiencing a specific adverse event will be tabulated by treatment period and for the whole study, categorizing events by body system, and MedDRA term. In the by-patient analysis, a patient having the same event more than once will be counted only once. Adverse events will be summarized by worst CTCAE grade within a patient.

Adverse events classified as CTCAE Grade 3 or higher; study-drug-related events; adrenal, hepatic, and renal events leading to special diagnostic evaluations; events leading to discontinuation from treatment; and SAEs will be considered with special attention.

No attempt will be made to reconcile data collected from the patient/caregiver-reported outcome instruments with adverse event reporting.

Hematological data will be summarized by treatment period and overall. Hematological data will be graded according to CTCAE severity grade. The frequencies of the worst severity grade observed will be displayed by worst CTCAE grade within a patient.

Serum biochemistry and urine data (including parameters for assessment of adrenal, hepatic, and renal monitoring – see [Section 6.3.1](#)) will be summarized by treatment period and overall. Values will be graded according to CTCAE severity grade, when applicable. For variables graded according to CTCAE severity grade, the frequencies of the worst severity grade observed will be displayed within a patient. For parameters for which a CTCAE scale does not exist, the frequency of patients with values below, within, and above the normal ranges will be summarized.

Urinalysis data will be listed and summarized by treatment period and overall, and will be checked for changes from baseline over time.

The results of an ultrasound to examine the kidneys and collecting system will be listed and abnormal results will be noted and investigated in terms of their relation to other relevant patient outcome measurement.

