13.2.2. Duration of Therapy

This open-label study is expected to generate at least 144 weeks of safety information. This information will supplement safety data obtained from the randomized, placebo-controlled, double-blind study (PTC124-GD-020-DMD), which has a planned treatment duration of 48 weeks.

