#### **3.3. Study Endpoints**

##### **Primary:**

- Safety profile characterized by type, frequency, severity, timing, and relationship to ataluren of any adverse events or laboratory abnormalities

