## 5.2. Subject Disposition

A summary of subjects who discontinued ataluren treatment prematurely or were removed from the study prematurely will be reported for overall subjects and a subgroup of ambulatory/non-ambulatory subjects at study entry. Reasons for treatment early discontinuations will be described.

Since the sponsor has decided to discontinue the Study 020e, subjects who discontinue the study due to this reason or complete the study per protocol will be considered as censored in the time to discontinuation analysis. The time to discontinuation (in weeks) is calculated as  $(\text{discontinuation date} - \text{first dose date} + 1)/7$  for subjects who discontinue from the study due to reasons other than sponsor's decision of termination the study or transitioning to commercial drug. For subjects who discontinue due to these reasons or complete the study, the censor time is  $(\text{discontinuation date} - \text{first dose date} + 1)/7$  and  $(\text{study completion date} - \text{first dose date} + 1)/7$ , respectively. Time to discontinuation will be assessed using Kaplan-Meier methods and the Kaplan-Meier curve will be displayed.

The protocol deviations will be summarized by type. A listing of protocol deviations will be provided.

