## **7. ANALYSIS CHANGES FROM PROTOCOL**

The supportive analyses on 6-minute walk test have been removed because they are not of the scientific interest any more after the early termination of the study. All paired t-tests have been removed.

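### Timing is part of the primary safety endpoint, but no adverse-event summary table in the SAP has a time dimension, and the loss of the protocol's by-period tabulation is not declared

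*SAP*

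**What the plan says.** SAP 3.3 and Protocol 3.3 give the same primary endpoint: "Safety profile characterized by type, frequency, severity, timing, and relationship to ataluren of any adverse events or laboratory abnormalities".

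Protocol 10.4.3 carries timing into the adverse-event analysis: "The frequency of patients experiencing a specific adverse event will be tabulated by treatment period and for the whole study".

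SAP 5.7.1 defines a treatment-emergent event by a single window running "from the day of a subject's first dose of study drug to 6 weeks after the last dose of study drug in this study". For the tables it says "The number and percentage of subjects experiencing a specific TEAE will be tabulated", and then lists organ class and preferred term, severity grade, and two orderings by frequency. The same layout is repeated for related, serious, Grade 3 or higher, discontinuation, hepatic/renal and common events. One exposure-adjusted rate per term divides all events by all days on drug, with 336 days counted as a year. None of these uses the onset date.

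SAP 7 lists the changes from the protocol. They are the removed supportive analyses of the 6-minute walk test and "All paired t-tests have been removed". The by-period adverse-event table is not mentioned. SAP 1 gives the SAP precedence wherever it conflicts with the protocol.

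**The concern.** The study's primary objective is long-term safety. For adverse events, the SAP plans a summary of type, frequency, severity and relationship, but none of timing. Since the SAP takes precedence, the narrower list is the one likely to be programmed, and section 7 gives a reader no sign that a protocol commitment has gone.

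A crude percentage and a pooled rate are the same whether events fall in the first weeks, are spread evenly, or appear only in the third year. Unequal follow-up adds to this. SAP 5.2 begins "Since the sponsor has decided to discontinue the Study 020e" and treats moving to commercial drug as a further reason for censoring. If patient-time is thinner late than early, early exposure dilutes any late excess in the pooled rate.

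**Working it through.** The documents contain no event-rate or power calculation on this point, so there is no figure of theirs to reproduce. The SAP's own constants agree: 48 × 7 = 336 days, and 144 weeks × 7 / 336 = 3.0 SAP years.

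**Inputs from the documents.** The upper bound is about 220 boys (SAP 3.4). Treatment lasts up to 144 weeks (Protocol 6.2.1). Rate = events / patient-years × 100 (SAP 5.7.1).

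**Assumed inputs.** There are 30 events of one term, each in a different boy. A boy present in a 48-week block contributes one full SAP year. Retention is either complete (220/220/220) or falls to 220/176/110. The documents give no event counts and no retention figures.

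**What the SAP would print, and what a by-block table would print**

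- Share of boys: 30/220 = 13.6% in every row.
- Pooled rate, full retention: 30/660 × 100 = 4.55.
- Pooled rate, attrition: 30/(220 + 176 + 110) × 100 = 30/506 × 100 = 5.93.

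| Retention | Events per block | Share of boys | Pooled rate | Rate per block |
|---|---|---|---|---|
| Full | 10 / 10 / 10 | 13.6% | 4.55 | 4.55 / 4.55 / 4.55 |
| Full | 2 / 4 / 24 | 13.6% | 4.55 | 0.91 / 1.82 / 10.91 |
| 220/176/110 | 13.0 / 10.4 / 6.5 (constant rate) | 13.6% | 5.93 | 5.93 / 5.93 / 5.93 |
| 220/176/110 | 10 / 10 / 10 | 13.6% | 5.93 | 4.55 / 5.68 / 9.09 |
| 220/176/110 | 2 / 4 / 24 | 13.6% | 5.93 | 0.91 / 2.27 / 21.82 |

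The constant-rate counts are 30 × 220/506 = 13.0, 30 × 176/506 = 10.4 and 30 × 110/506 = 6.5. The fourth row shows why each interval needs its own denominator: level counts conceal a doubling of the rate, 9.09/4.55 = 2.0.

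Under a constant rate and full retention, the binomial probability of 24 or more of 30 events falling in the last block (n = 30, p = 1/3) is about 2 × 10⁻⁷. With the assumed attrition (p = 110/506) it is about 2 × 10⁻¹¹. A pattern this far from constant would leave no trace in the planned tables.

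An extreme case with other assumptions points the same way. Twenty events, all in the last block, give a pooled 20/660 = 3.0 against 20/220 = 9.1 per 100 in that block. With 220/165/110 boys retained, the figures are 20/495 = 4.0 against 20/110 = 18.2.

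**The case against.** **Other safety data keep their timing.** Laboratory values are summarized by visit with shift tables (SAP 5.7.2), vital signs and ECGs are by visit (5.8.1, 5.8.2), and renal ultrasound has shift tables at each visit (5.8.10). Listings are planned for every CRF module, with separate ones for deaths, serious events, events leading to discontinuation and hepatic/renal events, and onset date is recorded (Protocol 8.3). All of this stands. A reader might infer that the SAP cannot show late harm at all, and the documents do not support that. What remains is narrower: a listing has no at-risk denominator and is not the tabulation that the protocol planned. Time to discontinuation (5.2) is not specific to any event. Age at loss of ambulation (5.8.4) uses one event, disease progression, as a functional outcome.

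**The protocol's term is undefined.** Section 10.4.3 does not say what a treatment period is. In Protocol 6.1.5 it is an interval, "at the end of each 12-week treatment period for inventory", and 7.11 uses it the same way. Table 3 of the protocol shows one treatment period beside post-treatment, and 7.23 speaks of one lasting 96 weeks. On the single-period reading, the protocol's own table would not separate early from late events. One therefore cannot say that the SAP removed an analysis certain to show late harm, nor that it did so deliberately. The gap against the endpoint, which names timing, does not depend on the reading.

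**Extension weeks are not weeks on drug.** Boys enter after a planned 48 weeks of ataluren or placebo. A table by extension week alone would mix first-year exposure in one group with second-year exposure in the other. This is correct and shapes the fix.

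**Study duration.** Protocol 13.2.2 states "This open-label study is expected to generate at least 144 weeks of safety information", whereas 6.2.1 gives 144 weeks as a maximum. It is tempting to read early termination as turning this into a contradiction that bears on the adverse-event tables. It does not: one passage describes what the study was expected to yield, the other each boy's treatment. They should be reconciled as a separate matter.

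**Conclusion.** The point holds for the adverse-event summary tables and no further. Timing is a named attribute of the primary endpoint, the protocol planned some tabulation finer than the whole study, the SAP has none, and section 7 does not say so. As planned, those tables give the same output for constant and late-emerging risk. In the illustration, a last-block rate of 10.91 (full retention) or 21.82 (attrition) per 100 patient-years sits behind pooled rates of 4.55 and 5.93.

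That the tables cannot distinguish the patterns follows from the formulas and needs no assumption. The sizes rest on assumed event counts, timing and retention, and say nothing about what happened in this study. The documents give no sign that harm did emerge late, and they do not say how many boys left for commercial drug. This should be corrected; it does not invalidate the safety analysis.

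**What to change.** In SAP 5.7.1, add tables of treatment-emergent events by onset interval for all, serious, Grade 3 or higher, treatment-related and hepatic/renal events.

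- Define the intervals explicitly, for example Weeks 0–48, >48–96 and >96, since Protocol 10.4.3 does not.
- For each interval, give the boys at risk, the patient-time and the interval-specific rate.
- State where events in the 6 weeks after the last dose are counted. They fall inside the event window, but the patient-years count only days on drug.
- Show the tables by prior double-blind arm (ataluren/ataluren, placebo/ataluren), a grouping SAP 5.8.4 already uses, or by time since first ataluren dose, because cumulative exposure differs by 48 weeks.
- Report the numbers exposed beyond 48 weeks, beyond 96 weeks and to Week 144.

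If the sponsor prefers not to add these tables, declare and justify the departure from Protocol 10.4.3 in SAP 7. Separately, reconcile Protocol 13.2.2 with 6.2.1.

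The cost is SAP wording and a few more tables from dates already collected. Late-interval estimates will rest on fewer boys and be imprecise, which the denominators will make visible.

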6.2. Study Drug Treatment

6.2.1. Duration of Treatment

In this study, treatment will comprise continuous daily treatment with ataluren for up to 144 weeks (~3 years). This study may be further extended by amendment until either ataluren becomes commercially available or the clinical development of ataluren in DMD is discontinued.

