7.2.5. Post-Treatment Visits

All patients who discontinue study drug, except patients switching to commercial ataluren, must return for a Post-Treatment Visit at the investigator site 6 weeks (± 7 days) after the last dose of study drug and the End of Treatment Visit, for final study-related evaluations. If the End-of-Treatment Visit occurs >6 weeks after the last dose of study drug, the Post-Treatment Visit does not need to be performed.

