### **3.4. Sample Size**

The sample size for this extension study is not based upon any formal statistical hypothesis, but its upper bound is determined by the requirement that patients must have participated in the previous Phase 3 study of PTC124 (PTC124-GD-020-DMD) in which ~ 220 patients are expected to be enrolled.

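### SAP 5.7.1 labels adverse-event rates as per 100 patient-years but uses a 48-week year, so each rate is 8.0% below the calendar-year rate for the same events and on-drug days

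*SAP*

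**What the plan says.** SAP section 5.7.1 gives the formula as "the incidence rate of the TEAE per 100 patient-year = (number of events/number of patient-years) \*100", to be tabulated by SOC and PT. It then defines the denominator: "The number of patient-years is defined as the sum of the number of days on study drug of all patients divided by 336". The next sentence makes the convention explicit: "That is, a year is defined as 48 weeks".

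The numerator has a wider window than the denominator. The same section defines a TEAE as an event that occurs or worsens from the "first dose of study drug to 6 weeks after the last dose of study drug in this study", whereas patient-years count only days on drug.

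The protocol does not supply the 48-week year. Its safety analysis section (10.4.3) describes no exposure-adjusted rate. Section 6.2.1 plans "continuous daily treatment with ataluren for up to 144 weeks (~3 years"), which is an approximation. SAP section 7, which lists changes from the protocol, does not mention the rate or its unit.

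**The concern.** A patient-year is ordinarily read as a calendar year of exposure. Under SAP 5.7.1 the words name a shorter unit, so a reader who takes the label at face value, or sets the rates beside calendar-year rates from elsewhere, will understate every one of them. The SAP also uses years in the ordinary sense for age (for example in 5.3 and 8.2), so one word carries two meanings in the document.

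Long-term safety is the primary objective, and its stated purpose is to add to the overall safety database, so comparison with other data is likely. These are also the only exposure-adjusted adverse-event summaries planned. Follow-up will be unequal: SAP 5.2 opens its censoring rule with "Since the sponsor has decided to discontinue the Study 020e" and also allows for transfer to commercial drug. Crude percentages therefore cannot stand in for a rate.

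The mismatch between the TEAE window and the on-drug denominator is a second, separate fault. Events in the 6 weeks after the last dose enter the numerator with no matching time below, which can only raise the rate. How much depends on the length of treatment and on how fully those 6 weeks are observed. Observation will not be uniform: Protocol 7.2.5 says "All patients who discontinue study drug, except patients switching to commercial ataluren, must return for a Post-Treatment Visit".

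**Working it through.** **Inputs**

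- Divisor: 336 days, stated as a 48-week year (SAP 5.7.1).
- TEAE tail: 6 weeks after the last dose (SAP 5.7.1).
- Planned maximum treatment: 144 weeks (Protocol 6.2.1).
- Upper bound on patients: about 220 (SAP 3.4).
- Calendar-year length Y: not given in the documents. Assumed 365.25 days, with 365 and 366 as the range.

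**1. Reproduce the plan's figure.** 48 × 7 = 336, an exact match. The divisor is deliberate.

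**2. Effect of the unit alone.** For E events and D on-drug days, the SAP rate is 100E/(D/336) and the calendar rate is 100E/(D/Y). Their ratio is 336/Y, whatever E and D are.

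| Y (days) | 336/Y | Rate is below calendar by | Patient-years overstated by |
|---|---|---|---|
| 365 | 0.9205 | 7.9% | 8.6% |
| 365.25 | 0.9199 | 8.0% | 8.7% |
| 366 | 0.9180 | 8.2% | 8.9% |

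Example: 50.0 × 0.9199 = 46.0.

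**3. On the study's own scale.** 144 weeks is 1008 days. The SAP makes this 1008/336 = 3.00 patient-years; in calendar time it is 1008/365.25 = 2.76. If all 220 patients were treated for 144 weeks, total exposure would be 220 × 1008 = 221,760 days, which gives 660 SAP patient-years against 607 calendar patient-years. With an assumed 100 events, the rates are 15.15 and 16.47 per 100. This is a ceiling: the study was stopped early, so actual exposure will be lower. The ratio of the two rates stays the same.

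**4. Adding the window mismatch.** Assume a constant event rate that continues through the 6 weeks after treatment. Let T be weeks on drug and f the share of those 6 weeks actually followed. Against a calendar rate with matching windows, the net factor is (T + 6f)/T × 0.9199.

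| T (weeks) | f = 0 | f = 0.5 | f = 1 |
|---|---|---|---|
| 24 | 0.920 | 1.035 | 1.150 |
| 96 | 0.920 | 0.949 | 0.977 |
| 144 | 0.920 | 0.939 | 0.958 |

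With f = 1 the two effects cancel when (T + 6)/T = 1.0871, that is T = 6/0.0871 = 68.9 weeks. Below that the printed rate is too high; above it, too low.

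**The case against.** The strongest reply is that nothing is hidden. The SAP prints the formula, the divisor and a plain definition of the year, and no other passage contradicts them. The documents also use 48 weeks as a nominal year elsewhere. The parent study's treatment period is 48 weeks, the protocol calls 144 weeks roughly 3 years, and its six-monthly weight-based adjustment (Protocol 6.1.4) is carried out at Weeks 24, 48, 72 and 120 (Protocol 7.2.3). The factor is one known constant that a reader can undo by multiplying by 1.087. It is also small beside sampling noise: assuming Poisson counts, the relative standard error is 1/√25 = 20% for 25 events and 1/√100 = 10% for 100. No table shells are available, so a footnote may be planned. Finally, the 6-week tail works in the opposite direction.

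Much of this stands as a limit on the harm. Rankings, ratios within the table and n (%) tables do not move. No test is at stake: SAP 3.4 says "The sample size for this extension study is not based upon any formal statistical hypothesis" and SAP 7 removes all paired t-tests.

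It does not remove the fault. Calling 144 weeks about 3 years is a loose description of duration and does not make 48 weeks a patient-year in a rate. A reader can rescale only if told the unit, and the SAP does not require the tables to show it. The 8% is systematic, so it does not average out as noise does. The tail is no justification for 336 either, because its effect varies with exposure and follow-up while the unit error is constant.

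**Conclusion.** The concern holds. As written, SAP 5.7.1 yields a rate per 100 patient-48-weeks and calls it a rate per 100 patient-years. For the same events and on-drug days, every SOC and PT rate is 8.0% below the calendar-year rate (7.9% to 8.2% for Y from 365 to 366 days). That figure depends only on the assumed length of a calendar year.

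The net departure from a matched-window calendar rate is a different quantity, and its sign cannot be settled from the documents. Under the constant-rate assumption the factor runs from 0.92 to 1.15 at 24 weeks on drug and from 0.92 to 0.96 at 144 weeks.

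This is a fault of unit and comparability in descriptive summaries of the primary endpoint. It does not threaten the study's validity, but it should be corrected.

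**What to change.** **Unit.** Divide total on-drug days by 365.25. If the 48-week unit is kept, name it per 100 patient-48-weeks in the SAP and on every table, with a footnote giving the definition. Either route costs one constant or one label in the SAP and table shells and needs no new data. The 365.25 divisor alone raises every rate by 8.7%; tables already produced can be rescaled by 1.087 or relabelled.

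**Windows.** As a useful but optional addition, give a supplementary rate whose numerator and denominator cover the same time. Two forms would serve:

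- on-drug events over on-drug days; or
- TEAEs over days from first dose to the earlier of last dose plus 42 days and last contact.

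This costs somewhat more: either a separation of on-drug from post-treatment events or a last-contact derivation, plus one further table by SOC and PT. The net change in the rates from doing both cannot be predicted from the documents.
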